## Palbociclib (IBRANCE)

## Study Number A5481128 NON-INTERVENTIONAL STUDY PROTOCOL

Protocol Version 2, August 30, 2021

				the proportion of patients with a duration less than or greater than/equal to 12 months.
Surgery	Chart review	Treatment characteristics	Medical history prior to index	The proportion of patients who had surgery prior to the index treatment.
Radiotherapy	Chart review	Treatment characteristics	Medical history prior to index	The proportion of patients who received radiation prior to the index treatment.
Index treatment regimen	iKM structured data + chart review	Eligibility criteria, Treatment characteristics	Study observation period	Patients' index treatment will be categorized based on the cohort descriptions in Section 8.1: PB+FUL CCI
Date of treatment initiation during the patient identification period (i.e., index date)	iKM structured data + chart review	Eligibility criteria, Treatment characteristics	Study observation period	The date of initiation with a PB+FUL or CCI during the study identification period. If the combination regimen consists of more than one drug with drugs given on different dates, the date of the first administration of any drug will be used. Patients who did not initiate a qualifying regimen during the patient identification period will be excluded from the study.
Treatment initiation by quarter	iKM structured data + chart review (derived)	Treatment characteristics	Study observation period	The proportion of patients who initiate treatment by quarter.
Index treatment end date(s)	iKM structured data + chart review	Treatment characteristics	Study observation period	Date of final treatment for each drug or regimen. It is possible that the patient's treatment stop date is not documented if the patient dies, is lost-to follow-up or is still on-therapy. The final treatment date, death date or end of study date will be used, whichever is earliest.
Index line of therapy (LOT)	iKM structured data + chart review (derived)	Treatment characteristics	Study observation period	LOT will be assigned based on the absolute chronologic order of regimens, based treatment start and stop dates. Specifically, first-line treatment designation will be assigned to the first treatment received after metastatic diagnosis. Line of therapy will advance with each subsequent regimen.
Mean and median duration of index therapy	iKM structured data	Treatment characteristics	Study observation period	The duration (in weeks) between the start and stop of the index treatment regimen. Findings will be summarized as the mean ( $\pm$ SD) and median (range) of values.
Number of cycles (index treatment)	iKM structured data	Treatment characteristics	Study observation period	The number of provider-documented therapy cycles received for the index treatment. Findings will be summarized as the mean ( $\pm$ SD) and median (range) of values. The number of patients with available data will be reported.
Index treatment schedule (cycle length and frequency)	iKM structured data + chart review	Treatment characteristics	Study observation period	The planned frequency cycle length of the index treatment. Findings will be summarized as the mean ( $\pm$ SD) and median (range) of values. The number of patients with available data will be reported.

PFIZER CONFIDENTIAL

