Real-world duration of treatment (rwDOT)	iKM structured data + chart review (derived)	Clinical outcomes	Study observation period	rwDOT will be defined as the interval (in weeks) between the start and stop index as documented in the iKM EHR database. Patients with ongoing treatment at the study observation period will be censored on the study end date or the last visit date available in the dataset, whichever occurred first. rwDOT will be analyzed using the Kaplan-Meier method with 95% CIs, and summary tables of the number of events and censored patients at 6, 12, 18, 24, 30, and 36 months.
Time to next treatment (TTNT)	iKM structured data +chart review (derived)	Clinical outcomes	Study observation period	TTNT will be defined as the interval (in weeks) between the start of the index treatment and the date of the next-line treatment as documented in the iKM EHR database. Patients who did not advance to the next treatment within the study observation period will be censored on the study end date or the last visit date available in the dataset, whichever occurred first. TTNT will be analyzed using the Kaplan-Meier method with 95% CIs, and summary tables of the number of events and censored patients at 6, 12, 18, 24, 30, and 36 months.

Provider-documented tumor assessments				

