### 8.7.2. Derived and transformed data

Some of the data elements needed for the study objectives will be derived from available data during the analysis phase of the study. Details about these calculations are provided along with the operational definition in **Table 2**. Prior to constructing these variables, the McKesson biostatistician will perform data validation activities. Data validation will continue and will consist of, but is not limited to, quality control checks for appropriate values, logical sequences and quantity of missing values.

Missing data will be identified and reported in the results tables as percentages for all variables. If there is a large amount of missing or illogical data, a decision to include, exclude or impute that variable will be subsequently made based on the study sponsor's decision.

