6 HANDLING OF MISSING VALUES

In the case of missing observations, the number and percentage of missing values will be reported. No imputation for missing values will be performed.

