7.2.2 Summary of Analyses

Table 2 presents an overview of the planned analyses for this study. As supported by the final sample size, each of the results tables and figures will be stratified to present the data for the stratifications defined in **Section 4.4**.

Table 2. Overview of study analyses

Analysis	Data source	Statistical method	Missing data
Baseline demographic and clinical characteristics	Structured + chart review data	Descriptive statistics	Missing values reported
Provider- and clinic-level characteristics	Structured data only	Descriptive statistics	Missing values reported
Treatment patterns	Structured + chart review data	Descriptive statistics	Missing values reported
Time to chemotherapy	Structured + chart review data	Kaplan-Meier methods	Patients without the event will be censored
Real-world duration of therapy (rwDOT)	Structured + chart review data	Kaplan-Meier methods	Patients without the event will be censored
Time to next treatment (TTNT)	Structured + chart review data	Kaplan-Meier methods	Patients without the event will be censored
Overall survival (OS)	Structured data + chart review data + LADMF/NDI	Kaplan-Meier methods	Patients without the event will be censored
Real-world time to tumor progression (rwTPP)	Structured data + chart review data + LADMF/NDI	Kaplan-Meier methods	Patients without the event will be censored
Real-world progression-free survival (rwPFS)	Structured data + chart review data + LADMF/NDI	Kaplan-Meier methods	Patients without the event will be censored

[figure not shown]
PFIZER CONFIDENTIAL

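### The plain mean and median duration of index therapy count cut-off dates as treatment stops, so this one descriptive row will usually read short

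*Protocol*

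**What the plan says.** Three entries in the variable table (Protocol section 8.3, Table 2; repeated in SAP section 5.4, Table 1) bear on this.

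- *Index treatment end date(s)* recognises that a stop may not exist: "It is possible that the patient's treatment stop date is not documented if the patient dies, is lost-to follow-up or is still on-therapy". It then fixes a date: "The final treatment date, death date or end of study date will be used, whichever is earliest". It does not say whether that date is a stop or a censoring date.
- *Mean and median duration of index therapy* is defined as "The duration (in weeks) between the start and stop of the index treatment regimen", summarised as mean (SD) and median (range). It has no censoring rule and no Kaplan-Meier step.
- *rwDOT*, a secondary endpoint, covers the same start-to-stop interval by Kaplan-Meier with 95% CIs and has a rule for those still treated: "Patients with ongoing treatment at the study observation period will be censored on the study end date or the last visit date" (whichever comes first).

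The SAP overview of analyses (section 7.2.2, Table 2) keeps this split. Treatment patterns get descriptive statistics. For rwDOT and the other time-to-event outcomes it says "Patients without the event will be censored".

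**The concern.** For a patient still on palbociclib plus fulvestrant at the data cut, or lost before it, the true duration is known only to exceed the observed time. The end-date row supplies a date anyway, and the duration row treats the interval to that date as complete. The result mixes finished durations with lower bounds and can only err downward.

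The report would then carry two figures for time on the same regimen, one of them shortened by when follow-up ended. Results are also to be stratified by many subgroups where sample size allows (Protocol 8.2.3; SAP 4.4). A stratum with more patients still on treatment could therefore look shorter in this row for that reason alone.

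**Working it through.** **Inputs from the documents.** Index dates run from 1 February 2016 to 31 December 2019, with cut-off on 30 June 2020 (Protocol 8.1). The final first-line cohort is 317 (Protocol Table 3).

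**Assumed, because the documents give no expected duration of therapy.** Durations T are exponential, index dates are even over the window, and there is no loss before cut-off. True medians are 11.2 and 27.9 months, plus 20 in between. The first two are trial PFS medians quoted in Protocol section 6, used only as stand-ins for scale.

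**Plan's own figure.** 31 December 2019 to 30 June 2020 is 182 days; 182 / 30.4375 = 5.98 months, which reproduces the stated 6-month potential minimum. The maximum is 1,611 days = 52.93 months. Potential follow-up F is therefore uniform on 5.98 to 52.93 months, a width of 46.95.

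**Formulas.** With λ = ln 2 / true median:

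- P(F > t) = 1 for t ≤ 5.98, then (52.93 − t) / 46.95.
- The plain median solves exp(−λt) × P(F > t) = 0.5.
- Share with no true stop: P(T > F) = [exp(−5.98λ) − exp(−52.93λ)] / (46.95λ).
- Plain mean = (1/λ) × [1 − P(T > F)].

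**Substitution for the median**

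- True 11.2: at t = 9.8, 0.545 × 0.919 = 0.50.
- True 20: at t = 14.3, 0.609 × 0.823 = 0.50.
- True 27.9: at t = 17.1, 0.654 × 0.763 = 0.50.

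| True median (months) | No stop at cut-off, of 317 | Plain median | Median short by | True mean | Plain mean |
|---|---|---|---|---|---|
| 6.0 | 29 (9.2%) | 6.0 | 0% | 8.7 | 7.9 |
| 11.2 | 71 | 9.8 | 12% | 16.2 | 12.5 |
| 20 | 127 | 14.3 | 28% | 28.9 | 17.3 |
| 27.9 | 161 | 17.1 | 39% | 40.3 | 19.8 |

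**The 6-month boundary.** Cut-off alone cannot truncate anyone before 5.98 months, so a true median up to about 6 is unaffected while the mean is still short. Earlier loss removes that protection. With 5% to 10% lost per year, a true median of 6.0 is reported as 5.8 to 5.6. With 10% to 20% per year, a true median of 5 comes out 6% to 12% short.

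**Sensitivity of the plain median, for true 11.2, 20 and 27.9**

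- Adding 5% to 10% yearly loss: 9.3 to 8.9, 13.4 to 12.5 and 15.8 to 14.6 months.
- Index dates loaded linearly early or late, or Weibull shape 0.8 to 1.3, each varied alone: 2% to 19%, 10% to 40% and 19% to 51% short. The smallest figure in each range is early accrual, the largest late accrual.

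**Check on the remedy.** In simulation with ongoing and lost patients censored, the Kaplan-Meier median returned the true value (true 12, 18, 24, 30 gave 12.0, 18.0, 24.0, 30.0). The plain medians without loss were 10.3, 13.5, 15.9 and 17.6.

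**The case against.** The strongest reply is that duration of therapy, as a stated objective, is rwDOT, and rwDOT is sound for ongoing patients. The plain row is not named in any objective, and the number and percentage of patients with ongoing index treatment is already to be reported. The table shells in SAP section 8 are not visible and may label the row properly. The size rests on assumed durations and accrual, and the 11.2-month stand-in comes from a trial in patients who had progressed on prior endocrine therapy. All of this stands. It limits the consequence but does not change what the row's definition produces.

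Two stronger readings are tempting, and the documents do not support them.

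- *Patients without a stop are left out, so the figure is shorter still.* A reader might infer this from SAP section 6, "No imputation for missing values will be performed", with Protocol 8.7.2 leaving the matter open: "a decision to include, exclude or impute that variable will be subsequently made". But the end-date row deals with exactly these patients and says which date is used. That specific rule governs, and once a date is assigned the value is not missing. The Protocol 8.7.2 sentence concerns variables with much missing or illogical data.
- *A reader could not tell whether they were left out.* The neighbouring cycle-count row promises "The number of patients with available data will be reported" and the duration row does not. However, reporting of missing values is promised generally (Protocol 8.7.2 and 8.7.3; SAP section 6 and Table 2), so an omission would show as a missing count.

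**Conclusion.** The point holds as a minor one. The end-date and duration rows, followed literally, summarise truncated times as completed durations. The direction does not depend on the assumptions: the mean is short if any patient is ongoing or lost. The median is short above about 6 months from cut-off alone, and below that with earlier loss. The size does depend on them. Under exponential durations, even accrual and no loss, the median is 12%, 28% and 39% short at true medians of 11.2, 20 and 27.9 months, and only about 2% short at 11.2 if accrual was early.

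A reader might infer that rwDOT is shortened too. The documents do not support that: its definition censors ongoing patients, and SAP Table 2 censors those without the event. Death on treatment is a real end of therapy, so using the death date is not part of the bias. Whether rwDOT counts death as an event deserves a sentence, but is a separate clarification.

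**What to change.** 1. Report duration of index therapy as the planned rwDOT Kaplan-Meier median with 95% CI.
2. Drop the plain row, or relabel it *observed time on treatment to data cut-off* and print the already planned number ongoing beside it.
3. In the end-date row of both documents, state that a date assigned to an ongoing or lost patient is a censoring date, not a stop.

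The cost is one removed or relabelled row and a clarifying sentence in each table. No new data or analysis is needed. The downside is that the simple mean is lost if the row is dropped; relabelling keeps it with its meaning made clear.

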## Palbociclib (IBRANCE)

## Study Number A5481128 NON-INTERVENTIONAL STUDY PROTOCOL

Protocol Version 2, August 30, 2021

Index treatment schedule changes	Chart review	Treatment characteristics	Study observation period	Index treatment schedule changes will be captured and reported as the proportion of patients with changes.
Index palbociclib treatment starting dose	iKM structured data + chart review	Treatment characteristics	Study observation period	
The actual index treatment starting palbociclib dosage received. If needed, the dose is automatically calculated with the EHR based on patient's body surface area or weight and dosage.
 
Findings will be summarized as the mean (<math>\pm</math> SD) and median (range) for all patients within the specified cohort. The number of patients with available data will be reported.

Reasons for palbociclib initiation of less than 125 mg/day	Chart review	Treatment characteristics	Study observation period	
For patients who initiated palbociclib at a dose lower than 125 mg/day, reasons will be captured and reported:
 
 
Age
 
Concomitant medications
 
Diagnosis
 
Due to line of therapy received
 
ECOG performance status score
 
Patient request
 
Presentence of comorbidities
 
To avoid toxicity
 
Other
 

Index palbociclib treatment dose/schedule changes	Chart review (derived)	Treatment characteristics	Study observation period	Index dose/schedule changes will be captured and reported as the proportion of patients with dose changes.
Reason for palbociclib dose changes	Chart review	Treatment characteristics	Study observation period	
Data for palbociclib dose change reason will exclusively come from chart review. Reviewers will be asked to select reason(s) as explicitly documented in patients' charts. If available, reason patients discontinued treatment will be abstracted:
 
 
Lack of response
 
Patient preference
 
Toxicity
 
Other
 
No information
 
 
Reviewers will specify other reasons; these will be reported if any represent <math>>5\%</math> of patients.

Reason for treatment discontinuation	Chart review	Treatment characteristics	Study observation period	
Data for discontinuation reason will exclusively come from chart review. Reviewers will be asked to select reason(s) as explicitly documented in patients' charts. If available, reason patients discontinued treatment will be abstracted:
 
 
Progression
 
Toxicity
 
Decline in performance status
 
Financial/insurance
 
Completed planned treatment
 
Death
 
Hospice
 
Patient preference (if other categories do not apply)
 

PFIZER CONFIDENTIAL

				Physician preference (if other categories do not apply) Other
Proportion of patients who advance/do not advance	iKM structured data + chart review (derived)	Treatment characteristics	Study observation period	The proportion of patients who advance and do not advance from the index treatment will be summarized as the count and percentage of the following: Patients with ongoing index treatment Patients who died following index treatment Patients who advanced to a subsequent treatment Patients who did not advance to a subsequent treatment for unknown reasons
Post-index treatment regimen	iKM structured data + chart review	Treatment characteristics	Study observation period	The regimen received by patients following discontinuation from the index treatment.
Time to chemotherapy	iKM structured data +chart review (derived)	Clinical outcomes	Study observation period	Time to chemotherapy will be defined as the interval (in weeks) between index treatment and start of chemotherapy as documented in the iKM EHR database. Patients with ongoing treatment at the study observation period will be censored on the study end date or the last visit date available in the dataset, whichever occurred first. rwDOT will be analyzed using the Kaplan-Meier method with 95% CIs, and summary tables of the number of events and censored patients at 6, 12, 18, 24, 30, and 36 months.
Real-world duration of treatment (rwDOT)	iKM structured data + chart review (derived)	Clinical outcomes	Study observation period	rwDOT will be defined as the interval (in weeks) between the start and stop index as documented in the iKM EHR database. Patients with ongoing treatment at the study observation period will be censored on the study end date or the last visit date available in the dataset, whichever occurred first. rwDOT will be analyzed using the Kaplan-Meier method with 95% CIs, and summary tables of the number of events and censored patients at 6, 12, 18, 24, 30, and 36 months.
Time to next treatment (TTNT)	iKM structured data +chart review (derived)	Clinical outcomes	Study observation period	TTNT will be defined as the interval (in weeks) between the start of the index treatment and the date of the next-line treatment as documented in the iKM EHR database. Patients who did not advance to the next treatment within the study observation period will be censored on the study end date or the last visit date available in the dataset, whichever occurred first. TTNT will be analyzed using the Kaplan-Meier method with 95% CIs, and summary tables of the number of events and censored patients at 6, 12, 18, 24, 30, and 36 months.

Provider-documented tumor assessments				
Provider-documented tumor assessment	Chart review	Clinical outcomes	Study observation period	
In prospective clinical trials, response is generally assessed according to Response Evaluation Criteria In Solid Tumors (RECIST) criteria. However, the parameters underlying these criteria are less reliably available in retrospective, observational studies. Instead, for this study, we will rely on provider documented assessments of response. No attempts will be made to mimic the RECIST guidelines.
 
Response assessments documented for the index treatment (depending on cohort). It is possible that patients have multiple response assessments in their charts during this period. All documented responses described in scan reports and progress notes (along with the associated note date) will be captured.
 
Response assessments will be classified as:
 
 
Complete response: Documented as “a complete response” to therapy; indication patient is in “remission”; “all lesions” have disappeared or “no evidence of disease”.
 
Response not otherwise specified (partial response or response not otherwise): any documentation of improved disease or responding disease not definitively classified as a complete response.
 
Stable disease: Documented as disease is stable (not progressed or not improved; e.g. Stable appearance of lobe nodules).
 
Mixed response: Combination of improved and worsened disease.
 
Progressive disease: Documented as disease has “progressed”; or worsening of disease.
 
Not evaluated: No documentation of status of disease.
 

Best overall response (BOR)	Chart review (derived)	Clinical outcomes	Study observation period	
Each patient will be assigned one BOR based on all recorded response assessments captured during chart review.
 
The responses will be ranked in the following order (from best to worst):
 
 
Complete response
 
Improved disease
 
Stable disease
 
Mixed response
 
Progressive disease
 
Not evaluated
 
 
The proportion of patients with each BOR category will be reported.

Date of provider-documented progression or recurrent disease	Chart review	Clinical outcomes	Study observation period	The date of provider-documented progression or recurrent disease as explicitly noted by a clinician in a scan report or progress note. Frequently, this will be the date the provider recorded evidence of progression, not

PFIZER CONFIDENTIAL

				necessarily the date the radiologic assessment was made.
Real-world complete, improved or stable disease rate (clinical benefit rate)	Chart review (derived)	Clinical outcomes	Study observation period	In real-world research, the parameters underlying response as defined by RECIST criteria are often unavailable. As such, this study will assess response to treatment as documented by providers and capture real-world assessments of response, including complete response, improved disease and stable disease. This measure will be similar to clinical benefit rate as defined by RECIST criteria.
Clinical outcomes				
Last USON visit date	iKM structured data + chart review	Clinical outcomes	Study observation period	Each patient's most recent visit date, prior to or on close of study observation period will be recorded. A visit is defined as a physician encounter with the practice where either treatment is given or vital signs are recorded. For patients with a death date, this last visit date should occur prior to the death date. This will not be reported separately; it will be used in calculating the patient's available follow-up time as a descriptive measure. available follow-up time = Integer (latest of last visit date or death date – index date +1)
Death date	iKM structured data, chart review + external sources	Clinical outcomes	Study observation period	Date of death will be captured from the iKM EHR, limited access death master file (LADMF), national death index (NDI) and, possibly, other commercial sources of death information (the study team is confirming the utility of these sources). If dates conflict among the sources, the NDI, followed by the LADMF date will be prioritized. If severe data discordance is observed (i.e., death is reported to occur prior to the index date), then the iKM death date will be used. Further information on the sources of death information is presented in Section 8.4 .
Follow-up duration	iKM structured data, chart review + external sources (derived)	Clinical outcomes	Study observation period	The duration between index and last follow-up date. Findings will be summarized as the mean ( $\pm$ SD) and median (range) for all patients within the specified cohort. The number of patients with available data will be reported.
Vital status	iKM structured data, chart review + external sources (derived)	Clinical outcomes	Study observation period	Patients without a date of death recorded in iKM, LADMF, NDI or other commercial sources of death information used for the study will be assumed to be alive at the end of the study. Those with a date of death in available records will be flagged as deceased. Further information on the sources of death information is presented in Section 8.4 .
Overall survival (OS)	iKM structured data, chart	Clinical outcomes	Study observation period	OS will be defined as the interval (in weeks) between index treatment and the date of death (any cause) as documented in the iKM EHR database, LADMF, NDI and other

	review + external sources (derived)			commercial sources of death records that may be used for this study. Patients who did not die within the study observation period will be censored on the study end date or the last visit date available in the dataset, whichever occurred first. OS will be analyzed using the Kaplan-Meier method with 95% CIs, and summary tables of the number of events and censored patients 6, 12, 18, 24, 30, and 36 months.
Survival rate	iKM structured data, chart review + external sources (derived)	Clinical outcomes	Study observation period	Survival rates will be provided along with the Kaplan-Meier OS analyses described above as survival rates at 6, 12, 18, 24, 30, and 36 months.
Real-world progression-free survival (rwPFS)	iKM structured data, chart review + external sources (derived)	Clinical outcomes	Study observation period	The rwPFS will be measured from the initiation of the index treatment to the date of progression or date of death due to any cause, censoring patients who are still alive at the end of the study observation period and did not progress at the last visit date. The rwPFS will be estimated in weeks using the Kaplan-Meier method with 95% CIs, and summary tables of the number of events and censored patients at 6, 12, 18, 24, 30, and 36 months.
rwPFS rate	iKM structured data, chart review + external sources (derived)	Clinical outcomes	Study observation period	PFS rates will be provided along with the Kaplan-Meier PFS analyses described above as PFS rates at 6, 12, 18, 24, 30, and 36 months.
Real-world time to tumor progression (rwTTP)	iKM structured data, chart review + external sources (derived)	Clinical outcomes	Study observation period	The rwTTP will be measured from the initiation of the index treatment to the date of provider-documented progression, censoring patients without evidence of provider-documented progression at the last visit date. The rwTTP will be estimated in weeks using the Kaplan-Meier method with 95% CIs, and summary tables of the number of events and censored patients at 6, 12, 18, 24, 30, and 36 months.

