				
(RECIST) criteria. However, the parameters underlying these criteria are less reliably available in retrospective, observational studies.²⁰ Instead, for this study, we will rely on provider documented assessments of response. No attempts will be made to mimic the RECIST guidelines.
 
Response assessments documented for the index treatment (depending on cohort). It is possible that patients have multiple response assessments in their charts during this period. All documented responses described in scan reports and progress notes (along with the associated note date) will be captured.
 
Response assessments will be classified as:
 
 Complete response: Documented as "a complete response" to therapy; indication patient is in "remission"; "all lesions" have disappeared or "no evidence of disease"). Response not otherwise specified (partial response or response not otherwise): any documentation of improved disease or responding disease not definitively classified as a complete response. Stable disease: Documented as disease is stable (not progressed or not improved; e.g. Stable appearance of lobe nodules). Mixed response: Combination of improved and worsened disease. Progressive disease: Documented as disease has "progressed"; or worsening of disease. Not evaluated: No documentation of status of disease.
Best overall response (BOR)	Chart review (derived)	Clinical outcomes	Study observation period	
Each patient will be assigned one BOR based on all recorded response assessments captured during chart review.
 
The responses will be ranked in the following order (from best to worst):
 
 Complete response Improved disease Stable disease Mixed response Progressive disease Not evaluated 
The proportion of patients with each BOR category will be reported.

Date of provider-documented progression or recurrent disease	Chart review	Clinical outcomes	Study observation period	
The date of provider-documented progression or recurrent disease as explicitly noted by a clinician in a scan report or progress note. Frequently, this will be the date the provider recorded evidence of progression, not necessarily the date the radiologic assessment was made.

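### The progression date for rwTTP and rwPFS may come from a scan report or a later note, with no clear rule between them; where the later note is used, the times can only lengthen.

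*Protocol*

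**What the plan says.** Protocol section 8.3, Table 2 defines the progression date as "The date of provider-documented progression or recurrent disease as explicitly noted by a clinician in a scan report or progress note". It then qualifies this: "Frequently, this will be the date the provider recorded evidence of progression, not" "necessarily the date the radiologic assessment was made". SAP section 5.4, Table 1 carries the same caveat.

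That date feeds two secondary endpoints. For the first, "The rwTTP will be measured from the initiation of the index treatment to the date of provider-documented progression". For the second, "The rwPFS will be measured from the initiation of the index treatment to the date of progression or date of death due to any cause". SAP section 5.1 defines both in the same way.

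The tumor-assessment row of the same table describes what was abstracted: "All documented responses described in scan reports and progress notes (along with the associated note date) will be captured". It puts worsening of disease in the progressive category and states: "No attempts will be made to mimic the RECIST guidelines".

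Section 8.3 (SAP section 5.4) also has a general rule that, among several values in a measurement window, the one nearest to treatment start is taken. Neither document has a tie-break specific to progression, gives a scan-to-note lag or plans a sensitivity analysis on this date. Protocol section 8.9 does not list the lag among the limitations.

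**The concern.** Two sources are allowed for the event date, and they do not err symmetrically. A note that reports a scan cannot be earlier than that scan. Choosing the note therefore either leaves the event time unchanged or lengthens it. This is bias rather than noise, so a larger cohort does not remove it.

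The exposure differs by endpoint. In rwTTP every event is a progression, so every event can be affected. In rwPFS only the progressions can be, because death dates carry no such lag.

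At stake are the rwTTP and rwPFS medians and the rates at 6 to 36 months, which the plan estimates in weeks. For conflicting death dates the plan does set out a source order. For progression, the tumor-assessment row may already hold an earlier scan report of the same event, and the plan does not say that its date should be used.

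**Working it through.** The plan states no expected median, event count or lag for these endpoints, so there is no figure of its own to reproduce.

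**Step 1. Does the general rule in section 8.3 settle the date?** Not clearly.
- It sits in a paragraph mainly about baseline and history variables.
- If it does govern outcomes, it selects the earlier of two explicit statements of progression. It does not reach a scan report that describes worsening without calling it progression. Such a report is classed as progressive disease in the tumor-assessment row, but it may not meet the requirement of an explicit clinician statement in the progression-date row.

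**Step 2. Size, closed form (upper bound).** Inputs from the documents:
- n = 317 first-line PB+FUL patients (Protocol Table 3)
- Median PFS of 11.2 months (palbociclib arm of the phase 3 trial in patients who had progressed on endocrine therapy)
- Median PFS of 27.9 months (PB+FUL arm of the randomized trial in treatment-naive, endocrine-sensitive patients)

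Both medians come from Protocol section 6 and are only illustrations for this cohort. Assumptions not in the documents are exponential times, a lag L of 1 to 4 weeks (0.23 to 0.92 months), and every event lagged.

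The true curve is S(t) = exp(−ln 2 · t / median). The observed curve is S(t − L), so the median moves by exactly L.

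| Quantity | True | L = 1 week | L = 4 weeks | Excess |
|---|---|---|---|---|
| Median 11.2 months | 11.2 | +0.23 | +0.92 | 2% to 8% |
| 6-month rate, median 11.2 | 0.690 | 0.700 | 0.730 | 1.0 to 4.0 points |
| 12-month rate, median 11.2 | 0.476 | 0.483 | 0.504 | 0.7 to 2.8 points |
| Median 27.9 months | 27.9 | +0.23 | +0.92 | 0.8% to 3.3% |
| 12-month rate, median 27.9 | 0.742 | 0.746 | 0.759 | 0.4 to 1.7 points |

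For comparison, the 95% half-width of a rate, ignoring censoring, is 1.96 · √(S(1 − S)/317). That is 5.5 points at S = 0.476 and 4.8 points at S = 0.742.

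**Step 3. Size, simulation.** The set-up was 317 patients, exponential times and censoring uniform over 6 to 53 months (from the identification period and the end of follow-up on 30 June 2020). Ten percent of events were deaths without lag (assumed), 50% or 100% of progressions were note-dated (assumed), and there were 500 runs per scenario. Medians were 11.2, 27.9 and 31.8 months, the last from the first-line phase II trial in Protocol section 6.

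| Lag | Shift in median, weeks (50% to 100% note-dated) |
|---|---|
| 1 week | 0.3 to 0.9 |
| 2 weeks | 0.9 to 1.8 |
| 4 weeks | 1.9 to 3.8 |
| 8 weeks | 3.6 to 7.3 |

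The 95% sampling half-width of the median was about 7 to 8 weeks at 11.2 months, 21 to 24 weeks at 27.9 months and 25 to 29 weeks at 31.8 months. The shift approached sampling error only with an 8-week lag, all progressions note-dated and the shortest median (7.3 against 7.9 weeks).

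**Step 4. Are scan dates in hand?** The tumor-assessment row names the date of the associated note. It describes no field for the date on which the scan was performed. Chart review ended in December 2020 (Protocol Table 1). Amendment 2 (Protocol section 4) removed the response endpoint because of the number of patients with non-evaluated tumor assessments. Scan-report dates may therefore exist for some events and not for others.

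**The case against.** The strongest reply is that this is a disclosed definition and not a mistake. The endpoint is provider-documented progression, the plan says it will not imitate RECIST, and the caveat about the date is printed in the table. That stands: the documents do not contradict themselves here, and dating by the clinician's record is a legitimate choice.

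Three stronger readings are tempting, and the documents do not support them.
- A reader might infer that progression is never dated by the scan. A scan report is one of the two named sources, and the caveat is only that the recording date is frequent.
- A reader might infer that imaging dates are already in the dataset. Only the associated note date is named, and assessments are limited to those documented for the index treatment.
- A reader might infer that both endpoints are known to be materially too long, or that comparisons are distorted. The direction is certain for each event dated from a later note, but the size is not known. Nothing shows that the lag differs between strata. A comparison with trials is optional and would need an amendment.

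It is also fair to say that the general rule in section 8.3 may already select the earlier date when a scan report and a note both state progression. If so, the gap narrows to reports of worsening not labelled as progression, and the documents do not show how common these are. The 11.2-month illustration comes from patients who had progressed on endocrine therapy; the 27.9-month figure is nearer to a first-line cohort and gives the smaller effect.

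None of this supplies a dating rule, a measurement of the lag or a line in the limitations.

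**Conclusion.** The point holds as a gap in the dating rule with a known direction and an unknown, probably modest, size. Where a later note is used although an earlier scan report of the same progression was abstracted, rwTTP and the progression part of rwPFS are shifted later.

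The figures of about 2% to 8% at a median of 11.2 months and 0.8% to 3.3% at 27.9 months are an upper bound for assumed lags of 1 to 4 weeks, since they take every event as lagged. If half the events are lagged, the effect is roughly half. With 317 patients this is mostly within sampling error, but it does not average out. The plan should state the rule and measure the lag where the data allow.

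**What to change.** In Protocol Table 2, SAP Table 1 and SAP section 5.1, state the following for rwTTP and rwPFS:

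1. The clinician's call decides whether there is a progression event.
2. Once progression has been called, the event date is the earliest abstracted scan-report date classed as progressive disease that falls after index and after the last non-progressive assessment, where such a date was captured.
3. Otherwise the event date is the note date.

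Report the share of events dated each way and the scan-to-note interval. Keep the note-date version as a sensitivity analysis. Add the remaining lag and its direction to Protocol section 8.9.

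The cost is a wording change in both documents and a re-derivation from dates already collected, as far as they exist; where none exists the rule falls back to the note date. The downsides are that rwTTP and rwPFS become slightly shorter and that, because scan-report dates may be incomplete, some events will keep the note date and the dating will be mixed. That is why the share dated each way has to be reported.
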